7.5.2.2 Secondary safety endpoints

The secondary safety endpoint is defined as the number of patients with drug related adverse events (AEs). This will be a part of the Safety analyses described in detail in [Section 7.8](#).

7.7 EXTENT OF EXPOSURE

The number of subjects who received a dose of trial drug will be tabulated. The amount of treatment received (actual and weight based) will be summarised by descriptive statistics (N, mean, SD, minimum, median, maximum) per visit and overall. Additionally, number of infusions administered overall per treatment arm will be displayed. Also, the duration of the infusion will be provided for each visit.

7.8 SAFETY ANALYSIS

All safety analyses will be performed based on the SAF following BI standards. No hypothesis testing is planned.

In addition, overall AE table and the frequency table of patients with at least one AE by MedDRA System Organ Class and Preferred Term will be prepared for AEs occurring between start date of study medication and Week 16 visit data (not including residual effect period).

All safety data analyses beyond Week 16 (for patients not receiving BI open-label treatment) will be based on SAF-OL.

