1.4 BENEFIT - RISK ASSESSMENT

The positive efficacy data obtained in GPP (trial 1368.11) confirms BI 655130's mechanism of action of effectively blocking the IL36 pathway thereby providing support for potential benefit in diseases where the IL36 pathway appears to contribute to disease. Furthermore, the clinical safety data support clinical studies in patients with repeat doses up to 20mg/kg IV qw.

There is no direct benefit for individual participants in this study, because efficacy of BI 655130 has not been demonstrated in AD and because some patients will initially be randomised to the placebo arm. Participation in this study may help to generate future benefit for larger groups of patients with atopic dermatitis if BI 655130 proves to be successful in treating this disease. In order to assess any future benefit for atopic dermatitis patients, it is critical to have a placebo control to address potential confounding factors, such as placebo effect, regression to the mean in endpoint scoring or potential investigator bias in safety and efficacy assessments. Patients who are initially randomized to placebo and do not respond will be given the opportunity to receive BI 655130 after the Week 16 primary analysis.

One subject in trial 1368.2 appeared to have an infusion reaction at a dose of 20 mg/kg, thus patients in this trial will be closely monitored for infusion reactions, including measurement of pulse and blood pressure prior to infusion and approximately 5 and 60 minutes after the end of infusion.

Humans with congenital absence of IL36R have no adverse clinical signs or symptoms, including susceptibility to infection or reactivation of chronic infections. Nonetheless, given this is the first trial in patients with atopic dermatitis, patients with active infection or certain chronic infections (HIV, HBV, TB) will be excluded.

Proprietary confidential information © 2020 Boehringer Ingelheim International GmbH or one or more of its affiliated companies

The mouse specific analogue of BI 655130 has been tested in embryo-fetal and fertility and early embryonic development studies. There was no evidence of effects on fertility or embryonic development (teratogenicity) in mice after administration of 10 or 50 mg/kg/dose.

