6. GENERAL ANALYSIS DEFINITIONS

6.1 TREATMENTS

For basic study information on the treatment to be administered, assignment to treatment, and selection of dose, cf. Section 4 of the CTP.

In the blinded treatment phase, all patients will receive either intravenous doses of 600mg of BI 655130 solution for infusion (at weeks 0, 4, 8, and 12), or Placebo.

At Week 16, all patients will be evaluated with the EASI Score. Non-responders (EASI < 75) will be re-allocated to receive BI open label trial drug from Week 16 through Week 28; they will be followed until Week 44. Responders (EASI >= 75) will be re-assigned to receive no further trial treatment but will be expected to come to all visits up to Week 28, when EOS visit is planned.

The following trial periods/phases are defined:

Table 6.1: Flow chart of trial period/phases

Trial phase	Description	Start (included)	End (excluded)
Screening phase	Screening	Date of informed consent	Date of start of first infusion of study drug (day 1).
Blinded Treatment phase	Randomised On-treatment period	Date of start of infusion of first study drug (Day 1)	Week 16 visit date + 1 day
Open label Treatment phase ¹	Re-allocation period (Either open label BI655130 or No treatment)	Week 16 visit date + 1 day	Date of EoS Participation visit + 1 day

Dates are defined individually per patient. If more than one date is associated with a specific visit, measurements associated with a specific date are assigned to a study analysis phase according to the rules specified in the table. An analysis phase will not extend beyond the start date of the following phase.

¹ Non-responders (i.e. EASI<75) at Week 16 will be re-allocated to BI655130 600mg IV open label and will continue in the trial until Week 44. Responders (EASI>=75) at Week 16 will be re-allocated to no treatment and will be observed until Week 28 or the day when they return to a 50% reduction in EASI score (EASI50) and start the treatment in the extension trial.

Patients who discontinue the treatment but will continue on trial visits will be included in analyses with the available data. For patients who discontinue trial prematurely only available data will be used in the analyses.

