For the final analysis of the trial to be performed once all patients have completed through the planned period, results will be summarized including the data from the reallocation period (Open-label Treatment phase). Results will be presented separately and in descriptive manner. The time windows for data presentation in this analysis are described in [Table 6.7: 1](#). In addition, analyses including the data from the double-blind period (initially used for the Primary Analysis) will be re-run after the final database lock.

To distinguish between assignment to trial periods/phases and AE assignments, please, refer to [Table 6.1:2](#).

Table 6.1: 2 AE assignment to analysis treatment groups

Randomised treatment	EASI75 response at Week 16	Open-label period	AE assignment to analysis treatment group
PLACEBO	Responder	No Treatment	AE that occurred between first randomised study drug intake and min[(EoS visit date), (last randomised study drug administration date + 112 days)] will be analysed under PLACEBO. AEs occurring later will be listed only.
PLACEBO	Non-Responder	BI 655130 Treatment	AE that occurred between first randomised study drug intake and Week 16 visit date (excluding) will be analysed under PLACEBO. AEs occurring later will be analysed under Open-label BI Treatment.
BI 655130	Responder	No Treatment	AE that occurred between first randomised study drug intake and min[(EoS visit date), (last randomised study drug administration date + 112 days)] will be analysed under BI 655130. AEs occurring later will be listed only.
BI 655130	Non-Responder	BI 655130 Treatment	AE that occurred between first randomised study drug intake and Week 16 visit date (excluding) will be analysed under BI 655130. AEs occurring later will be analysed under Open-label BI Treatment.

Treatment groups up to Week 16 will be labelled as follows:

- **"Speso 600 mg IV q4w"** (i.e., patients randomised to BI 655130 600 mg)
- **"Placebo"** (i.e., patients randomised to Placebo)
- **"Overall Total"** (across treatments: Placebo and BI 655130 600 mg), where appropriate.

Treatment groups for the efficacy analysis after week 16 will be labelled as follows:

- **"Open-label treatment: No Treatment"**
 - **"Placebo"** (i.e., patients randomised to Placebo in the double-blind treatment period and who did not receive an open-label BI 655130 treatment starting from Week 16 (V7))

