6.7 BASELINE, TIME WINDOWS AND CALCULATED VISITS

Measurements reported with date and time and taken prior to start of administration of trial treatment will be considered pre-treatment values. Measurements reported with a date only (and no time) and taken on the day of first administration of trial treatment will also be considered pre-treatment values. These pre-treatment values will be assigned to visits according to the nominal visit number as recorded on the eCRF or as provided by the laboratory. For definitions used in Safety analyses, refer to [Section 7.8](#).

Baseline, unless otherwise specified, is defined as the last measurement collected prior to the start of administration of the trial treatment.

Measurements taken after start of administration of trial treatment will be considered either on- or off-treatment values based on the definition in [Section 6.1](#), and will be assigned to visits for statistical analysis, if applicable, as defined below.

Analysis of AE data, concomitant medication or non-drug therapies will not be based on visits. Therefore, no assignment to time windows will be necessary for such data.

For derivation of the last value on treatment, minimum value on treatment, and maximum value in the trial phase, all values from the relevant phase (whether or not collected in any time window; see [Table 6.1: 1](#) for definition of the trial periods/phases) will be considered; these will be derived for analysis of laboratory and vital signs data. For identification of potentially clinically significant abnormal laboratory values, all values (whether or not selected in any time window) before the date of EoS Participation visit will be considered.

A graphical analysis of the ALT and total bilirubin will be performed (so called eDISH plot) based on the available data obtained during the on-treatment period.

All other safety, efficacy and biomarker measurements will be assigned to visits based on extended time windows around the planned visit dates, defined relative to the day of first trial treatment (which is scheduled for Visit V2). These extended time windows are defined in [Table 6.7: 1](#).

Table 6.7: 1 Time windows for assignment of efficacy, safety lab, vital signs, and biomarker measurements to visits for statistical analysis of the double-blind treatment period

Visit number / name	Visit label	Planned day	Time window (Days)				
			Window (per CTP)	Start (per CTP)	End (per CTP)	Start (extended)	End (extended)

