7.2 CONCOMITANT DISEASES AND MEDICATION

Analyses of concomitant diseases and medication will be based on the RS.

Concomitant diseases will be coded according to the most recent version of MedDRA.

Concomitant medication will be coded according to the most recent version of the World Health Organisation – Drug Dictionary.

Concomitant diseases which are present at start of the study, as well as characteristics of the trial disease, will be descriptively summarized by treatment.

A medication will be considered concomitant to treatment, if it

- is ongoing at the start of trial treatment or
- starts within the on-treatment period (see [Section 6.1](#) for a definition of study analysis phases).

Concomitant medication use will be summarised with frequency and percentage of patients by ATC3 class and preferred name. Summaries will be presented for:

- historical medication taken before the first study drug administration of the double-blind period (i.e., the start and stop dates are before the date of the first study medication infusion)
- concomitant medication that started before the double-blind treatment (i.e., concomitant medication start date was prior to first study treatment administration)
- concomitant medication started and taken within the double-blind period (from the day of the first treatment administration to the date of the Week 16 visit – 1 day)
- concomitant medication that started on or after the Week 16 (V7) visit date (i.e., concomitant medication start date was on the Week 16 visit date or thereafter)

The frequency and percentage of patients with previous medication for AD will be displayed as per data collected in the eCRF (i.e., separately for topical, non-topical, and non-topical/non-drug therapies). Frequencies by preferred name and treatment arm will be displayed.

Concomitant use of non-drug therapies will be summarized with frequency and percentage. Summaries will be presented for

- historical non-drug therapies taken before the first study drug administration of the double-blind period (i.e., the start and stop dates are before the date of the first study medication infusion)
- concomitant non-drug therapies that started before the double-blind treatment (i.e., concomitant non-drug therapy start date was prior to first study treatment administration)
- concomitant non-drug therapies started and taken within the double-blind period (from the day of the first treatment administration to the date of the Week 16 visit – 1 day)

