7.8.3 Vital signs

The analyses of vital signs (blood pressure, pulse rate, body temperature and body weight) will be descriptive in nature and will be performed for double-blind period and re-allocation period separately.

Descriptive statistics of vital signs over time and for the difference from baseline (see [Section 6.7](#)) will be provided by treatment, including summaries of the last value during the respective period (double-blind or re-allocation), the minimum value during respective period, and the maximum value during respective period (see [Table 6.1: 1](#) for definition of the trial periods/phases).

Clinically relevant findings in vital signs data will be reported as baseline conditions (at screening) or as AEs (during the trial) if judged clinically relevant by the investigator, and will be analysed as such.

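### For patients dosed open-label at Week 16, the SAP's phase boundary puts the two post-infusion vital-sign readings into the double-blind last/min/max; separately, SAP 7.8 names SAF-OL for patients whom SAF-OL excludes

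*SAP*

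**What the plan says.** **Phases.** Each phase in SAP Table 6.1: 1 has an included start and an excluded end. The blinded phase ends, and the open-label phase starts, at "Week 16 visit date + 1 day".

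**Dosing and readings.** Protocol 3.1 and 6.2.3 give non-responders their first open-label infusion at Week 16 (V7). Flow Chart footnote 5 and Protocol 5.2.2 schedule vital signs at every infusion visit before the dose and about 5 and 60 minutes after the infusion ends. Protocol 1.4 presents "measurement of pulse and blood pressure prior to infusion and approximately 5 and 60 minutes after the end of infusion" as part of close monitoring for infusion reactions.

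**Summaries.** For last, minimum and maximum of laboratory and vital-sign data, SAP 6.7 uses "all values from the relevant phase (whether or not collected in any time window"; the same parenthesis points to Table 6.1: 1. SAP 7.8.3 asks for "summaries of the last value during the respective period (double-blind or re-allocation), the minimum value during respective period", plus the maximum, by treatment, and again cites Table 6.1: 1.

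**Other data on the Week 16 date.** For placebo non-responders, Table 6.1: 2 says "AE that occurred between first randomised study drug intake and Week 16 visit date (excluding) will be analysed under PLACEBO", with later events counted as open-label; active non-responders are treated alike. SAP 7.2 counts double-blind concomitant medication "from the day of the first treatment administration to the date of the Week 16 visit – 1 day".

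**By-visit display.** In Table 6.7: 2, row V7.1 (Week 16OL) starts the day after the Week 16 visit date. Its footnote covers vital signs taken after the responder assessment. It mentions the first open-label treatment but names Week 16 (V7) as the visit.

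**Analysis set.** SAP 7.8 says "All safety data analyses beyond Week 16 (for patients not receiving BI open-label treatment) will be based on SAF-OL". SAP 6.3 restricts SAF-OL to patients who received study medication after re-allocation and makes it the main safety set for that period.

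**The concern.** The infusion that begins open-label treatment falls on a date that the SAP counts as blinded. For a patient randomised to placebo, the first readings ever taken after BI 655130 would then contribute to the placebo column of the double-blind last/min/max table. The matching re-allocation table would begin only at V8 and so omit the readings around the first open-label infusion. AEs of re-dosed patients and concomitant medication are cut on the other side of the same date, so this is not one convention applied throughout the SAP.

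Safety and tolerability are stated as the main objective and are reported descriptively only (Protocol 2.1.1). The treatment label on a reading is therefore most of what these tables convey, and the planned placebo group is only 15 patients.

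The SAF-OL sentence raises a separate problem: a programmer who follows it literally is sent to a set that contains none of the patients it names.

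**Working it through.** The documents state no figure on this point, so there is none to reproduce. The check applies the Table 6.1: 1 rule to the scheduled readings.

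1. **Rule.** Blinded if Day 1 ≤ date < Week 16 date + 1; open-label if date ≥ Week 16 date + 1. With V7 on Day 113, the V7 pre-dose, 5-minute and 60-minute readings all have date 113, which is below 114, so all three are blinded-phase. The first open-label-phase readings are at V8 (Day 141).

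2. **Scheduled readings after the first dose, up to and including the Week 16 date, for a patient dosed at V7:** V2 post-infusion 2; V3 1; V4, V5 and V6 3 each = 9; V7 pre-dose 1; V7 post-infusion 2. Total 2 + 1 + 9 + 1 + 2 = 15. Two follow open-label drug: 2/15 = 13.3%.

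3. **Last value.** In scheduled order, the final blinded-phase reading is the V7 60-minute reading. This holds for every patient who is dosed at V7 and has the full schedule. If Table 6.1: 1 split the day at the infusion, 13 readings would remain and the last would be the V7 pre-dose reading.

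4. **Extremes (illustration, assuming exchangeable readings without ties).** The minimum comes from the two readings with probability 2/15 = 13.3%, and the maximum likewise. At least one extreme does with probability 1 − (13/15)(12/14) = 25.7%. Leaving out the two Day 1 post-infusion readings gives 2/13 = 15.4% and 1 − (11/13)(10/12) = 29.5%. Counting the V2 pre-dose reading as well gives 2/16 = 12.5% and 1 − (14/16)(13/15) = 24.2%.

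5. **Re-allocation summary.** Four infusions (V7 to V10) × 2 = 8 scheduled post-infusion readings. The two at V7 are missing: 2/8 = 25%.

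6. **Patients affected.** These are all non-responders dosed at V7. The documents give no EASI75 or dropout rates. Purely as an assumption, take EASI75 rates (active/placebo) from 20%/10% to 50%/15%, 0 to 20% stopping before Week 16, and no re-dosing of those who stop.
   - Placebo: from 15 × 0.85 × 0.8 = 10.2 to 15 × 0.90 = 13.5 of 15.
   - Active: from 30 × 0.5 × 0.8 = 12.0 to 30 × 0.8 = 24.0 of 30.

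7. **SAF-OL.** Membership requires study medication after re-allocation. A responder re-allocated to no treatment fails that test; a non-responder dosed open-label passes. The group named in the 7.8 sentence therefore has no members in the set assigned to it.

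**The case against.** The best answer to the main point is the V7.1 footnote. It is specific to vital signs, sits on the Week 16OL row, and suggests that the authors saw the issue and meant to separate these readings. That may well hold for the by-visit table, so it cannot be said that the readings appear as placebo data everywhere. However, the footnote names V7 while its row starts a day later. If the readings do stay in V7, the SAP 6.7 same-day rule (worst value selected) could also bring one into the Week 16 display. On either reading, last/min/max ignores visit windows and follows Table 6.1: 1, so the footnote does not alter it.

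A reader might also take the SAP 6.1 sentence containing "measurements associated with a specific date are assigned to a study analysis phase according to the rules specified in the table" as a general rule that phases are assigned by date. It is conditional on a visit having more than one date, so it does not say that. The inference rests on the date boundaries in the table itself.

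The comparison with AEs and concomitant medication has limited force: data types may reasonably be cut differently, and pre-dose Week 16 assessments belong in the blinded phase. The comparison shows only that no uniform convention explains the vital-sign result.

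The practical stakes are modest. A clinically relevant vital-sign finding is reported as an AE, infusion reactions are summarised as AESIs, and Table 6.1: 2 assigns a re-dosed patient's AE on the Week 16 date to open-label. Individual values are listed. It would be wrong to infer that a reaction to the first open-label infusion is attributed to placebo, or that data are lost.

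On SAF-OL, the wording is probably a slip. Table 6.1: 2 already says how untreated responders' AEs are handled, and the opening rule of SAP 7.8 keeps these patients in the SAF.

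**Conclusion.** As written, the SAP puts two post-open-label vital-sign readings per patient dosed at V7 into the double-blind last/min/max and omits them from the re-allocation last/min/max. This is 2 of 15 scheduled readings on one side and 2 of 8 post-infusion readings on the other. The effect on the last value needs only the full schedule, same-day dosing at V7, and same-day readings taken in scheduled order. The percentages for the extremes also need exchangeability, and the patient counts rest on assumed rates.

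The effect is confined to descriptive vital-sign tables. AEs (including the drug-related AE endpoint), AESIs and efficacy are unaffected, as are laboratory, PK and ADA samples, which are scheduled before the infusion. SAP 6.1 refers to an ADS Plan for technical detail; it was not available, and actual programming may differ.

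The SAF-OL sentence is a wording contradiction that loses no data. A smaller inconsistency lies within SAP 6.3: membership speaks of medication after the Week 16 visit, while treatment assignment counts from that visit. It matters only for a patient whose sole open-label dose is at Week 16.

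Both points are worth correcting; neither affects the trial's efficacy conclusions.

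**What to change.** - **Table 6.1: 1.** For patients dosed open-label at V7, keep pre-dose Week 16 vital signs in the blinded phase. Assign post-infusion readings to the open-label phase, using the nominal pre-/post-dose label or clock time if recorded.
- **Tables 6.7: 1 and 6.7: 2.** Align the windows with this split and reword the V7.1 footnote, for example: *Vital signs recorded at Week 16 following the first open-label infusion belong to Week 16OL (V7.1); pre-dose readings belong to Week 16 (V7).*
- **Table 6.1: 2.** The date-based AE cut can stay, with a note that AEs are cut by date and Week 16 vital signs by infusion.
- **SAP 7.8.** State that post-Week-16 safety uses SAF-OL for patients who received open-label BI 655130, and the SAF for all others still under observation. Deleting *not* alone would leave the second group covered only by the general SAF sentence. Tying the set to drug actually received also covers early stoppers: Flow Chart footnotes 3 and 16 leave open whether they are re-dosed.
- **SAP 6.3.** Define SAF-OL by at least one open-label infusion at or after the Week 16 visit.

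The cost is wording in SAP 6.1, 6.3, 6.7 and 7.8 and minor programming, with no new assessments. The protocol already schedules the three readings as separate time points; the sponsor should confirm that the label is carried in the eCRF data.
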